8.2 SAMPLE SIZE DETERMINATION

The planned sample size is a minimum of 4 patients (2 per arm) and a maximum of 48 (24 patient's maximum per arm) based on the 3+3 design detailed in [3.1.2](#). An expansion of six additional patients can occur at the MTD in each arm as noted in [3.1.2](#). Estimates for sample size

are based on the assumption that all dose levels will accrue a maximum of patients, thus sample size is likely over-estimated. We anticipate accrual will require 30 months.

8.3 POPULATIONS FOR ANALYSES

All enrolled patients that initiate treatment with radiation will be considered evaluable for toxicity, unless they are removed from protocol treatment for a reason other than a DLT (such as illness unrelated to radiation). Patients that complete at least one post-treatment PSA will be considered evaluable for biochemical control and biochemical relapse free survival. Patients that complete QoL measures at 3 months will be considered evaluable for these measures.

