3.2 QUESTIONNAIRES (FOR ENGLISH SPEAKING PATIENTS ONLY)

(For English speaking patients only because questionnaires are not validated in other languages.)

Questionnaires will be collected on this trial, typically prior to visiting with the physician at each visit or within 1 week prior at the appropriate time points ([Appendix B](#)). Questionnaires may be completed in paper or electronically, but every effort will be made to have each patient complete questionnaires in the same format.

The timing of collection is noted on the study calendar in section [3.3](#).

The total time anticipated to complete all questionnaires below is 20 minutes.

Once data are abstracted, questionnaires will be maintained in the research chart (print or electronic). If stored, electronically, these files will have restricted access and be accessible only to members of the study team. In the event that questionnaires are stored electronically, paper copies will be shredded.

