3.3 STUDY CALENDAR

Procedure	Screening	Baseline ¹	Active RT treatment (2-4 weeks)	Follow Up, Months ⁷		
				1	3	6, 9, 12, 15, 18, 21, 24
RT treatment			X			
Medical History/Records	X					
Confirmation of Pathology	X					
Physical exam, vital signs, ECOG	X	X		X		
CBC with differential and platelet count		X				
Biochemical profile ²		X				
PSA	X	X			X	X ⁵
Testosterone		X			X	X ⁵
HIV	X					
CD4+ T-cell count for HIV positive patients	X					
Lymphocyte phenotype TBNK		X		X	X	X
Adverse Events		X	X	X	X	X
Concomitant Medications		X	X	X	X	X
mpMRI	X					X ⁸
Whole body bone scan or 18F-NaF PET/CT imaging ⁹	X					
CT of the abdomen and pelvis (if clinically indicated)	X					
Blood for correlative studies		X	X ³	X	X	X ⁵
Urine for correlative studies		X	X ³	X	X	X ⁵
Questionnaires ⁶		X				X ⁴
Archival tissue (if available, blocks or sections from prostatectomy or biopsies will be requested)		X				
Contact by phone call, e-mail or other NIH approved remote communication platform every 3 months once off treatment and unable to return for visits				X	X	X

1. Tests done at screening do not need to be repeated on baseline if performed in designated time frame prior to start of treatment
2. Biochemical profile: electrolytes, creatinine, BUN, alkaline phosphatase, ALT, AST, total and direct bilirubin
3. Sampling within 24 hours after the last dose of irradiation.
4. Every 6 months after treatment for 24 months
5. Every 3 months after radiation treatment for 24 months
6. Questionnaires: Expanded Prostate Cancer Index Composite (EPIC-26), SHIM, AUA-SI, PROMIS Depression SF4a, PROMIS Anxiety SF4a, PROMIS Psychological Impact Positive SF 4a, Decision Regret Scale. If the patient receives ADT, before initiation of ADT and within one week before starting radiation if ADT initiated more than one month prior to radiation. For English speaking patients only.

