7. +/- 1 week for 1 month visit, +/- 2 weeks for 3 and 6 month visits. +/- 4 weeks for next visits. If subjects are not able or willing to come to NIH to FU visits, they will be followed every three months remotely (by phone call, e-mail for adverse events or other NIH approved remote communication platform), further tumor therapy and lab results. Lab results from outside laboratories are accepted. A clinical evaluation may be completed remotely with a member of the study team to determine if the physical exam, vital signs and ECOG may be omitted. A subject may be referred to a local providers for further assessment at the discretion of the investigator after a remote assessment (e.g., finding that requires clinical assessment/follow up). Subjects may also be referred to their local provider for labs. If biochemical failure per **6.3.1** is identified, the second measurement will be obtained for confirmation, ideally at the NIH Clinical Center. Imaging may be delayed, but will be completed as soon as feasible. Collection of research blood or urine will be omitted or collected in a delayed fashion.
8. Only at the 6 month follow up time point.
9. Scans may be omitted if eligibility can be determined from MRI or other imaging results including 18F-DCFPyL.

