8.3.1 Definitions

Evaluable for toxicity: All patients will be evaluable for toxicity from the time of their first treatment with radiation, unless they are removed from protocol treatment before the end of the assessment period for a reason other than a DLT (such as illness unrelated to radiation).

Evaluable for response: Only those patients who complete radiation and have PSA measured after radiation will be considered evaluable for response. These patients will have their response classified according to the definitions stated earlier.

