8.4.3 Analysis of the Secondary Endpoint(s)

- Define the toxicity profile of image-guided, focally dose escalated prostate bed radiation in patients with a local or regional recurrence of prostate cancer after prostatectomy. All AEs except grade 1 with attribution to protocol treatment will be collected in tabulated way and analyzed.
- The rate of PSA control (biochemical progression free survival, bPFS) will be estimated by the Kaplan-Meier survival analysis and effects of clinical variables on bPFS will be assessed by the Cox proportional hazards model.
- The quality of life scores will be summarized at baseline and for each visit. Linear mixed effects model will be used to model quality of life scores at baseline and during and after treatment in which random intercept and random slope are used to account for patient-specific trajectory of quality of life scores. Changes of quality of life scores during and after treatment will be calculated from the estimated linear mixed effect model. The

similar analytical approach will be performed for depression scores and correlated with quality of life scores.

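### The quality-of-life evaluable set depends on a 3-month form that the study calendar does not schedule, and the one regret comparison written sets a percentage against its own complement

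*Combined protocol and SAP*

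**What the plan says.** **Evaluable set.** Section 8.3 states: "Patients that complete QoL measures at 3 months will be considered evaluable for these measures". It is the only quality-of-life population in the plan. The formal definitions in 8.3.1 cover toxicity and response only, the latter as "Only those patients who complete radiation and have PSA measured after radiation will be considered evaluable for response".

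**Schedule.** Section 3.2 says questionnaires are collected "typically prior to visiting with the physician at each visit", but limits this to the appropriate time points and adds "The timing of collection is noted on the study calendar in section" 3.3. The questionnaire row of that calendar is marked at baseline and in the column for months 6 to 24. Footnote 4 gives the frequency: "Every 6 months after treatment for 24 months". The treatment, month-1 and month-3 cells are empty. Footnote 6 adds pre-ADT and pre-radiation timings for patients on ADT, all of them before radiation. Footnote 7 sets the visit windows: plus or minus "2 weeks for 3 and 6 month visits".

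**Analysis.** Section 8.4.3 says "The quality of life scores will be summarized at baseline and for each visit", and that a linear mixed model will "model quality of life scores at baseline and during and after treatment". The next sentence again refers to change during treatment.

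**Regret.** The first bullet of Section 8.4.5 names two time points, enrollment and the end of follow-up, and hypothesizes that effective salvage reduces regret. The comparison it then writes is the percentage of patients with regret against the percentage without.

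**The concern.** A population definition should be satisfiable by the data the protocol collects. Here it is not. Patient-reported outcomes (SHIM, AUA Symptom Index, EPIC-26) are a stated secondary objective. If the conflict stands, someone must choose the quality-of-life population once the data exist, which is the choice a prespecified definition is meant to remove.

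For regret, the hypothesis concerns change over time and its relation to successful salvage. A comparison of two percentages that must sum to 100 in the same patients addresses neither. It could also yield a very small P value that a reader mistakes for evidence on the hypothesis.

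**Working it through.** **1. The plan's own figure.** Section 8.2 gives a maximum of 48. Three dose levels × 6 patients + 6 in expansion = 24 per arm; × 2 arms = 48. It reproduces and is not in dispute.

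**2. Scheduled forms.** Every 6 months for 24 months gives months 6, 12, 18 and 24. Month 3 is not among them. Calendar footnote 5 sets a separate 3-monthly frequency for PSA, testosterone, blood and urine and is not attached to questionnaires, so the calendar distinguishes the two frequencies.

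**3. Could a month-6 form serve as the month-3 form?** Take month 3 as day 91 and month 6 as day 182, each ± 14 days.
- Month-3 window: days 77 to 105.
- Month-6 window: days 168 to 196.
- Gap: 168 − 105 = 63 days, or 9 weeks. Section 3.2 allows a form up to 1 week before the visit, which leaves 8 weeks.

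It cannot. On-schedule patients who meet 8.3 as written: 0 of up to 48. With the definition tied to scheduled forms: up to 48, less non-English speakers (Section 3.2 limits questionnaires to English speakers) and dropouts.

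**4. Scores during treatment.** The active-treatment cell of the questionnaire row is empty and the footnote 6 additions precede radiation. Scheduled on-treatment scores: none.

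**5. The regret comparison.** With p the proportion with regret, p − (1 − p) = 2p − 1. This is a function of p alone, and testing it against zero tests p = 0.5. Section 1.2.3 gives regret of 10–20% after upfront treatment. At n = 48:

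| With regret | Without | 2p − 1 | Exact binomial P for p = 0.5 |
|---|---|---|---|
| 5 | 43 | −0.79 | about 1 × 10⁻⁸ |
| 10 | 38 | −0.58 | about 6 × 10⁻⁵ |

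These results arise whether regret rose, fell or stayed the same. The plan also gives no Decision Regret Scale cut-off for classing a patient as having regret.

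**6. What a paired change could estimate.** The 95% CI half-width for a mean paired change, in units of the SD of the change, is t(0.975, n − 1)/√n.
- n = 48: 2.012/6.928 = 0.29 SD. This needs a month-24 form from every patient.
- n = 36 (illustrative, a quarter missing): 2.030/6 = 0.34 SD.
- n = 24 (one full arm, or half of all patients): 2.069/4.899 = 0.42 SD.

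**The case against.** **The calendar may be the slip, not Section 8.3.** A month-3 visit exists, Section 3.2 speaks of each visit, 8.4.3 twice expects on-treatment scores, and 8.1.2 hypothesizes a decline lasting several months, which an early form would help to show. This stands: the documents do not say which text is wrong. Section 3.2 makes the calendar govern collection, but that does not prove 8.3 is the error. The supportable request is to reconcile the texts.

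**The analyses do not need the 8.3 set.** Section 8.4.3 does not restrict its summaries or model to it, and both can run on the scheduled forms. This also stands. A reader might infer that the quality-of-life objective is lost; it is not. The hypothesis of return to baseline by 2 years can be described from months 6 to 24.

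**The regret bullet should be read whole.** If the percentages are reported at both named time points, the change in p can be recovered. That is fair, and it shows a before/after intent. But the bullet does not write that comparison, does not pair patients, and compares nothing by salvage outcome.

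**Missing forms after recurrence.** Recurrence is an off-study criterion in 3.7.2, so a reader might infer that patients whose salvage fails will have almost no later forms, and try to count them. The documents do not support such a count. Biochemical failure needs two PSA values at least a month apart (6.3.1, 6.3.2, calendar footnote 7), so a patient is not confirmed as failing at the first raised value. The 75% control rate in the précis carries no time horizon, so failures cannot all be placed within 24 months. What holds is qualitative: patients who recur may lack later forms.

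**Conclusion.** Both parts hold as wording errors.

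The 8.3 definition and the calendar cannot both be followed. Read together they give an empty on-schedule set (0 of up to 48) for a descriptive secondary objective, and 8.4.3 refers to on-treatment scores that are not scheduled. The result rests on the calendar governing timing, as 3.2 says, and on nominal visit days.

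The regret comparison reduces to 2p − 1 and cannot address its own hypothesis. That objective is exploratory, and enrollment and month-24 forms are already scheduled, so the fault lies in the written comparison and not in collection.

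A reader might infer that rewording the comparison makes the salvage question answerable. It does not. Because recurrence can end follow-up, the overall month-24 change may over-represent controlled patients, and any split by biochemical control has the same weakness.

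The MTD, DLT rules, escalation and sample size are unaffected.

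**What to change.** Reconcile 8.3 and 8.4.3 with the calendar before analysis.

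- **8.3.** The repair that needs no new collection is to define quality-of-life evaluable as at least one scheduled post-treatment form (month 6, 12, 18 or 24). Require a baseline form only for change-from-baseline summaries, since the mixed model can use patients without one.
- **8.4.3.** Delete the reference to scores during treatment in both sentences.
- **If early or on-treatment forms were intended,** correct the calendar instead. That means added collection.
- **8.4.5.** Replace the comparison sentence with the paired within-patient change in Decision Regret Scale score from enrollment to month 24, reported as an estimate with 95% CI and the number of forms. Show months 6, 12 and 18 as well. Using the score avoids the missing cut-off.
- **Limitation to add in 8.4.5.** Recurrence is an off-study criterion, so patients who recur may lack later forms. This limits the overall month-24 change as well as any split by biochemical control. Such a split should be descriptive only and made at a common scheduled visit.

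Cost: one sentence in 8.3, one word deleted twice in 8.4.3, and one sentence replaced plus a limitation in 8.4.5. On the no-new-collection route there are no added visits or forms.

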8.3.1 Definitions

Evaluable for toxicity: All patients will be evaluable for toxicity from the time of their first treatment with radiation, unless they are removed from protocol treatment before the end of the assessment period for a reason other than a DLT (such as illness unrelated to radiation).

Evaluable for response: Only those patients who complete radiation and have PSA measured after radiation will be considered evaluable for response. These patients will have their response classified according to the definitions stated earlier.

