3.1.1 Dose Limiting Toxicity

The DLT period includes treatment period (4, 3 or 2 weeks depending on Dose Level) and the 3 following weeks. DLT is defined as any of the following:

- Grade 3 rectal, small bowel, or urinary toxicity that does not resolve to Grade 2 or less within 4 days with appropriate medical management.
- Other grade 3 in-field toxicities attributable to RT that do not resolve to Grade 2 or less within 4 days with medical management.
- Delays of more than one week in completing radiation treatment due to toxicity (cumulative duration of delay over the course of the entire treatment).

Additionally, toxicities that occur more than 3 weeks after completion of treatment and during the 24 month follow up period will be followed and scored but will not be used for escalation with the following exception. If Grade ≥ 4 late bowel or bladder injury is observed in 2 patients at any Dose level, dose escalation will be terminated and the dose below that dose level in which the toxicity was observed will be considered the MTD. Early and late toxicities used for assessment of DLTs should be attributable (possible, probable or definite) to radiation. Changes in sexual and erectile function will not be considered a DLT. MTD will be determined for each Arm separately.

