If a patient did not experience DLT and did not finish treatment, he will not be evaluable for toxicity and will be replaced in the dose level.

If patients develop side effects considered DLT, they will be taken off protocol treatment and may receive additional radiation as needed in standard fractionation to complete the treatment.

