3.7.1 Criteria for removal from protocol therapy

- Completion of protocol therapy
- Participant requests to be withdrawn from active therapy
- Unacceptable Toxicity as defined in section [3.1.1](#)
- PI discretion

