8.4.4 Safety Analyses

Adverse events will be coded as per the CTCAE v4.0. Each AE will be coded once for each patient based on the maximum severity during the assessment period. The relationship of AEs to study intervention will be recorded in addition to the onset date, end date, severity, expectedness, and outcome.

Dose-limiting toxicities are defined as follows (during treatment and within the first three weeks after treatment):

- Grade 3 rectal, small bowel, or urinary toxicity that does not resolve to Grade 2 or less within 4 days with medical management
- Other grade 3 in-field toxicities attributable to radiation that do not resolve to Grade 2 or less within 4 days with medical management
- Delays of more than one week in completing radiation treatment due to toxicity (cumulative duration of delay over the course of the entire treatment).

Additionally, toxicities attributable to radiation after the DLT assessment period (3 weeks after radiation is completed) will be followed and scored but will not be used for escalation with the following exception. If Grade ≥ 4 late bowel or bladder injury (late toxicity is defined as occurring >90 days after completion of radiotherapy) is observed in 2 patients in any Dose level group, dose escalation will be terminated and the dose below that dose level in which the toxicity was observed will be considered the MTD. Early and late toxicities used for assessment of DLTs should be attributable (possible, probable or definite) to radiation. Sexual and erectile dysfunction as a result of radiation will not be considered a DLT. Note that MTD will be determined for each Group separately.

Dose-limiting toxicities are defined as per section **3.1.1**.

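### The only toxicity population defined leaves out irradiated patients who stop for a non-DLT reason, and no all-treated safety set is named for the secondary toxicity profile or the AE summary

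*Combined protocol and SAP*

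**What the plan says.** Section 8.3 starts from all enrolled patients who begin radiation and counts them as evaluable for toxicity "unless they are removed from protocol treatment for a reason other than a DLT (such as illness unrelated to radiation"; that illness is its only example. Section 8.3.1 repeats the definition with a time limit: "unless they are removed from protocol treatment before the end of the assessment period for a reason other than a DLT". Section 3.1.2 says of a patient who had no DLT and did not finish treatment that "he will not be evaluable for toxicity and will be replaced in the dose level". No other toxicity or safety population is defined.

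On timing, section 3.1.1 states: "The DLT period includes treatment period (4, 3 or 2 weeks depending on Dose Level) and the 3 following weeks".

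Section 3.7.1 gives four grounds for leaving protocol therapy: completing it, the patient's wish ("Participant requests to be withdrawn from active therapy"), toxicity as defined in 3.1.1, and PI discretion.

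Safety and tolerability is a secondary objective (1.1.2, 8.1.2). For its analysis, 8.4.3 says: "All AEs except grade 1 with attribution to protocol treatment will be collected in tabulated way and analyzed". Neither that sentence nor the AE summary in 8.4.4 names an analysis set.

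The late Grade 4 or higher rule appears twice. In 3.1.1 it applies when "late bowel or bladder injury is observed in 2 patients at any Dose level"; in 8.4.4, when the injury "is observed in 2 patients in any Dose level group, dose escalation will be terminated".

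Section 6.1 documents AEs from the first study intervention without an evaluability condition. Beyond 30 days after the last treatment it requires only serious, related events.

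**The concern.** Replacing a patient so that an escalation decision rests on complete DLT information is ordinary in a 3+3 design. Describing toxicity is a different task, and its natural denominator is everyone who received the study radiation. The plan has one definition for both.

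The exclusion is not confined to reasons unrelated to treatment. In 3.7.1 the only toxicity ground for removal is the DLT definition. A man who finds the schedule hard to bear below that threshold can leave only by his own request or at PI discretion, and both are non-DLT reasons. For example, a Grade 3 rectal event that settles to Grade 2 within 4 days is not a DLT under 3.1.1. If he then withdraws, he falls outside the only defined toxicity set and his Grade 3 event goes with him. At stake is whether the secondary toxicity profile describes all exposed patients or only those who finished or had a DLT.

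**Working it through.** **1. The plan's own figure.** Section 8.2 gives a maximum of 24 per arm and 48 in all. Three dose levels of 6 plus an expansion of 6 gives 3 × 6 + 6 = 24, and 2 × 24 = 48. It reproduces exactly, so it contains no allowance for replaced patients.

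**2. How many patients could be affected.** The documents give no non-evaluable fraction; 5%, 10% and 15% are assumptions.
- If 48 caps enrolment, the patients outside the set number 48 × 0.05 = 2.4, 48 × 0.10 = 4.8 or 48 × 0.15 = 7.2, that is about 2, 5 or 7.
- If 48 must be evaluable, those exposed number 48/0.95 = 50.5, 48/0.90 = 53.3 or 48/0.85 = 56.5, rounded up to 51, 54 or 57.

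**3. Whether the time limit in 8.3.1 helps.** Taking its assessment period to be the DLT period, the window closes 3 weeks after radiation ends. Every stop during the course falls inside it, so 8.3 and 8.3.1 exclude the same mid-course stoppers. Read literally, both also catch completers, because 3.7.1 lists completion as a removal reason, it is not a DLT, and it comes 3 weeks before the window closes. That cannot be intended.

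**4. Effect on one dose level.** Take 6 evaluable patients with 2 events and one dropped patient.
- Evaluable only: 2/6 = 33%.
- All exposed, dropped patient had the event: 3/7 = 43%.
- All exposed, dropped patient did not: 2/7 = 29%.

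For scale, the background acute Grade 2 or higher rates in 1.2.1 are 21% GI and 14% GU. In 6 patients these give 6 × 0.21 = 1.3 and 6 × 0.14 = 0.8 expected events. They come from the cited randomised trials, not from this regimen.

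**5. When the loss biases the profile.** With k dropped patients beside 6 evaluable, the all-exposed rate is (6 × q0 + k × q1)/(6 + k), where q0 and q1 are the event probabilities in evaluable and dropped patients. Take q0 = 20% (assumed).
- q1 = 20%: 20.0%, no bias.
- q1 = 50%: k = 1 gives (1.2 + 0.5)/7 = 24.3%; k = 2 gives (1.2 + 1.0)/8 = 27.5%.
- q1 = 80%: k = 1 gives (1.2 + 0.8)/7 = 28.6%; k = 2 gives (1.2 + 1.6)/8 = 35.0%.
- q1 = 0%: k = 1 gives 1.2/7 = 17.1%, so exclusion would then overstate toxicity.

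**6. The late rule under either counting.** The chance of at least 2 events in n patients is 1 − (1 − p)^n − n·p·(1 − p)^(n−1). No Grade 4 or higher rate is given; section 1.2.1 has only late Grade 3 or higher rates (GU 7%, GI 2%). The values of p are assumptions.

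| p | 6 patients | 7 patients | 8 patients |
|---|---|---|---|
| 2% | 0.6% | 0.8% | 1.0% |
| 5% | 3.3% | 4.4% | 5.7% |
| 10% | 11.4% | 15.0% | 18.7% |

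One event among 6 evaluable patients plus one in a replaced patient counts as 1 or as 2, depending on who is counted. The rule acts at 2.

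**The case against.** The best reply is that the exclusion was meant only for escalation. Section 3.1.2 pairs non-evaluability with replacement in the dose level, 8.3.1 refers to an assessment period, and the criterion in each place is a DLT. Since the text read literally would drop completers, it needs a purposive reading, and DLT evaluability is the obvious one. This is plausible. Even so, the definition stands under the populations for analyses, uses the unqualified phrase evaluable for toxicity, and has no companion set. An analyst following the document has nothing else to apply.

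Three stronger readings are tempting, and the documents do not support them.

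- A reader might infer that the late Grade 4 or higher count omits replaced patients. Sections 3.1.1 and 8.4.4 count patients at a dose level with no evaluability condition, and a replaced patient was treated at that level.
- A reader might infer that such patients vanish from all toxicity reporting. Section 8.4.3 speaks of all AEs apart from grade 1, 6.1 collects AEs regardless of evaluability, and 7.4.1 has the PI review AE data on each patient. Leaving therapy (3.7.1) is also separate from leaving the study (3.7.2), so follow-up continues.
- A reader might infer that the schedules will look better tolerated than they are. That requires dropped patients to have more toxicity than the rest. The only example of removal is an unrelated illness, and the most troublesome intolerance is already a DLT and stays counted. Step 5 shows that the direction can go either way.

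Precision is poor in any case: exact 95% intervals are about 4–78% for 2/6 and 10–82% for 3/7. That limits what one patient can change in a descriptive table, but it does not justify leaving exposed patients out of it.

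**Conclusion.** The point holds in this form. The plan defines one toxicity population, suited to the DLT count, and names none for the secondary toxicity profile or the AE summary. If the defined set is used there, exposed patients are omitted, and those who withdraw with sub-DLT toxicity make the omission potentially informative.

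One dropped patient beside 6 evaluable moves a dose-level rate of 33% to 43% or 29%, depending on whether he had the event. Across the trial, an assumed 5–15% non-evaluable fraction would affect about 2 to 7 of 48 patients. The true number and the direction of any bias cannot be had from the documents. The 3+3 count and the replacement rule are not in question. For the late rule the finding is only that the set should be made explicit. The change should be made before the toxicity tables are produced.

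**What to change.** - In 3.1.2, 8.3 and 8.3.1, rename the existing set DLT-evaluable and state that it serves only the escalation decisions.
- Add a safety set of all patients who received at least one fraction. Use it for the toxicity profile in 8.4.3 and the AE summary in 8.4.4, by assigned dose level, with fractions received listed. Say that a replaced patient stays in it and remains in follow-up.
- State in 3.1.1 and 8.4.4 that the late Grade 4 or higher count covers all patients treated at the dose level, which is what the present wording most naturally means.
- Reconcile 8.3 with 8.3.1 on the time limit, and both with the listing of completion as a removal reason in 3.7.1, so that completers are plainly included.

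The cost is protocol and SAP wording. No new data are needed for the acute profile, because AEs are documented from the first intervention. After 30 days only serious, related events must be recorded, which should still serve a Grade 4 or higher count. The downside is that reported toxicity rates may change slightly and may be less favourable.

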6.3 RESPONSE CRITERIA

For the purposes of this study, patients should be re-evaluated for response every 3 months after treatment with a serum PSA measurement as per the study calendar. Response will be assessed based on PSA.

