6.3.2 Biochemical Progression-Free Survival

Biochemical progression free survival (bPFS) will be evaluated on this trial as a secondary endpoint. bPFS is defined as the duration of time from start of treatment to time of PSA progression or death, whichever occurs first. PSA progression (also known as biochemical failure) is defined based on elevation of PSA beyond 0.1 ng/dL. A total of 2 rising PSA values separated by at least 1 month are required to document biochemical recurrence. If the PSA remains elevated, the date of failure will be backdated to the first PSA measurement that exceeded 0.1 ng/dL. Only PSA values collected at the NIH Clinical Center will be used to evaluate disease status given the variability in ranges obtained in different laboratories.

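### Sections 8.3 and 8.3.1 set different populations for the PSA outcome, and both leave out a death before the first PSA that section 6.3.2 counts as a bPFS event

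*Combined protocol and SAP*

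**What the plan says.** Section 8.3: "Patients that complete at least one post-treatment PSA will be considered evaluable for biochemical control and biochemical relapse free survival".

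Section 8.3.1: "Only those patients who complete radiation and have PSA measured after radiation will be considered evaluable for response". It sends the reader back to the earlier definitions. Those are in section 6.3, which states "Response will be assessed based on PSA" and contains both biochemical control and failure (6.3.1) and bPFS (6.3.2).

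Section 6.3.2: "bPFS is defined as the duration of time from start of treatment to time of PSA progression or death, whichever occurs first". It adds a restriction on the data source: "Only PSA values collected at the NIH Clinical Center will be used to evaluate disease status".

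The study calendar (3.3) shows the first post-treatment PSA at month 3, with the schedule "Every 3 months after radiation treatment for 24 months". Footnote 7 to the calendar accepts outside laboratory results for men who cannot return.

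Section 3.1.2: "If patients develop side effects considered DLT, they will be taken off protocol treatment and may receive additional radiation as needed in standard fractionation".

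Section 8.4.3 names Kaplan-Meier and Cox methods for bPFS but no analysis set.

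**The concern.** The plan gives two denominators for one outcome and no statement of which applies, so the choice could be made after the data are seen. Each rule also requires something that happens after treatment starts, namely a PSA, although the bPFS clock has been running since the first day and death is one of its events. The men retained must all have survived to a PSA.

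Section 8.1.2 expects bPFS to compare favourably with published salvage series. With at most 24 men per arm, one or two exclusions can move the rate by several points.

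**Working it through.** **1. The plan's own figure.** Section 8.2 gives at most 24 per arm and 48 in all. Three dose levels × 6 + 6 in expansion = 24, and × 2 arms = 48, so the figure reproduces. No target or precision is stated for bPFS.

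**2. The rules side by side.**

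| Patient | 8.3 | 8.3.1 | 6.3.2 |
|---|---|---|---|
| Dies before first PSA | excluded | excluded | event |
| Stops radiation for toxicity, later has a PSA | included | excluded, unless further standard-fraction radiation counts as completing | followed from start |
| DLT in the 3 weeks after finishing radiation, later has a PSA | included | included | followed from start |
| Alive, no qualifying PSA | excluded | excluded | followed from start, never assessed |

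The first row contradicts the endpoint under both rules. The second row is where the two rules differ.

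**3. Early deaths.** With n treated, true bPFS S and complete follow-up otherwise, excluding k early deaths gives S·n/(n−k). The values of S are illustrations: about 75% is the PSA control quoted in the précis, and 62-80% is the 5-year range in section 1.2.1.

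- n = 24, S = 75% (18 event-free): k = 1 gives 18/23 = 78.3% (+3.3 points); k = 2 gives 18/22 = 81.8% (+6.8).
- n = 48, S = 75% (36 event-free): k = 1 gives 36/47 = 76.6% (+1.6); k = 2 gives 36/46 = 78.3% (+3.3).
- S from 62% to 80%, k = 1: +2.7 to +3.5 points at n = 24, and +1.3 to +1.7 at n = 48.

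The documents give no rate of death before month 3. If it is assumed to lie between 0.25% and 2%, the expected number in 48 is 0.12 to 0.96. The chance of at least one is 1 − 0.9975^48 = 11% to 1 − 0.98^48 = 62%.

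**4. Men who do not complete radiation (only if 8.3.1 governs bPFS).** Excluding k of n shifts the estimate by (k/n)(S_rest − S_stop). For k = 2, n = 24 and S_rest = 75%:

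| S_stop | Shift (points) |
|---|---|
| 0% | +6.2 |
| 50% | +2.1 |
| 75% | 0 |
| 100% | −2.1 |

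The documents give no rate of stopping. A rough proxy is the sum of the acute Grade 3 or higher GU and GI rates in section 1.2.1, 2% + 0.5% = 2.5%, which gives 48 × 0.025 = 1.2 men. Those rates come from standard treatment, and not every such event stops radiation.

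**5. Where to censor men without a PSA.** Censoring at last contact would count unassessed time as progression-free. Suppose n = 24, true bPFS is 75%, and two men have no qualifying PSA but are contacted to 24 months. The estimate is then (0.75 × 22 + 2)/24 = 77.1% (+2.1 points). With four such men it is (0.75 × 20 + 4)/24 = 79.2% (+4.2). Censoring at start of treatment avoids this.

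**The case against.** Section 8.3 is the only rule that names relapse-free survival, and it keeps a man who stopped for toxicity once he has a PSA. Section 8.3.1 speaks of response, which can be read as the categories in 6.3.1 and not as bPFS. This stands, so the reach of 8.3.1 over bPFS is an ambiguity. The conflict remains direct for biochemical control, which 8.3 names and 6.3.1 defines as a response category.

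A reader might infer that both rules drop the men with DLT and so inflate bPFS. The documents do not support that:

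- Only 8.3.1 requires completion.
- The DLT window runs to 3 weeks after treatment (3.1.1), so some men with DLT will already have finished.
- Others may finish in standard fractionation (3.1.2), and the plan does not say whether that counts as completing.
- DLT is not among the off-study criteria (3.7.2), so PSA follow-up can continue.
- The number of DLTs is therefore not the number of exclusions, and step 4 shows that the shift has no fixed sign.

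Nor is the absence of PSA failures before month 3 a product of these rules. Failure cannot be seen before the first PSA in any population, and this matters little at 1 and 2 years.

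Finally, bPFS is a descriptive secondary endpoint in a phase I study, and early deaths may be few or none. That limits the consequence but does not remove the contradiction.

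**Conclusion.** The point holds in two parts. First, 8.3 and 8.3.1 give different denominators for the PSA outcome, and 8.4.3 does not choose between them. Second, either rule discards a death before the first PSA that 6.3.2 defines as an event, and this can only raise the estimate, by about 1.3 to 3.5 points per death over 24 to 48 men and bPFS of 62-80%. These sizes assume complete follow-up otherwise, and how often such deaths occur is not known from the documents.

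The loss of non-completers depends on reading 8.3.1 as governing bPFS, and the direction of that bias is unknown. Dose escalation and the MTD are not affected.

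**What to change.** Replace the two evaluability sentences with one rule and cite it in 8.4.3:

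- Analyse bPFS in all patients who receive at least one fraction, from start of treatment.
- Count death as an event, including death before the first PSA.
- Censor event-free patients at the last qualifying PSA, or at start of treatment if alive with none, and report how many have none. Censored at time zero, these men do not move the Kaplan-Meier estimate, but they stay visible in the accounting.
- State that stopping treatment is neither an exclusion nor in itself an event.
- Keep completers with a PSA as a supportive analysis, and say whether finishing in standard fractionation counts as completing.
- Define a qualifying PSA by reconciling 6.3.2 (NIH Clinical Center values only) with footnote 7 of the study calendar (outside results accepted).

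The cost is protocol and SAP wording. No extra visits, samples or patients are needed.
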